## Statistical Analysis Plan

Sponsor:

Protocol number:

Moreover, in order to compare the two groups of patients, a t-test on the change of weekly mean of cries at last Week will be performed. In case of data not normally distributed, a Wilcoxon/Mann-Whitney test will be used.

- Number of infections of the respiratory system, gastrointestinal system, urinary system or skin during the study period.

Number of infections will be described on the ITT population, even if infections are defined using safety parameter. In fact, an infection will be defined as an Adverse Event with SOC equal to "Infections and Infestations".

The frequency and proportion of patients who reported at least one infection will be summarized and presented by category, System Organ Class and Preferred Term.

- Evacutive frequency

Frequency and consistency of stools are collected daily in the diary.

Stool frequency will be evaluated as the mean of total daily stools reported per week. Mean changes from baseline (i.e. mean of the first Week) to the mean of the selected week will be analyzed.

Summary statistics of mean stool frequency per week will be provided by means of descriptive statistics for continuous data.

- Consistency of the fecal mass

Stool consistency will be evaluated as the number and the proportion of patients who reported at least one stool sample of each type per week, according to Bristol scale. Patients could report more than one stool consistency per day (according to the number of daily stools): all the information collected will be analyzed.

Other data from patients' diary will be analyzed:

- Infant's mood

Infant's mood (calm, asleep, agitated, irritable) is collected daily in the diary and will be evaluated as the number and the proportion of infants who reported at least one mood of each type per week.

- Infant's sleep

Duration of sleep (in minutes) will be collected daily in the diary during the entire study period. The average daily duration will be defined as the mean duration of all sleeps during the day (i.e. sum of episodes' duration/number of sleeps during the day).

Weekly mean will be defined as the mean of the calculated average daily durations during the selected week and will be described by means of descriptive statistics for

	Statistical Analysis Plan
	Sponsor:
	Protocol number:

continuous data. Mean changes from baseline (i.e. mean of the first Week) to the mean of the selected week will be analyzed too.

- **Infant's temper**

Duration of temper episodes (in minutes) will be collected daily in the diary during the entire study period. The average daily duration will be defined as the mean duration of all temper episodes during the day (i.e. sum of episodes' duration/number of temper episodes during the day).

Weekly mean will be defined as the mean of the calculated average daily durations during the selected week and will be described by means of descriptive statistics for continuous data. Mean changes from baseline (i.e. mean of the first Week) to the mean of the selected week will be analyzed as well.

- **Infant's feeding**

Feeding time (in minutes) will be collected daily in the diary during the entire study period. The average daily duration will be defined as the mean feeding time during the day.

Weekly mean will be defined as the mean of the calculated average daily durations during the selected week and will be described by means of descriptive statistics for continuous data. Mean changes from baseline (i.e. mean of the first Week) to the mean of the selected week will be analyzed also.

Information about way of feeding will be only listed.

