## 1. INTRODUCTION

### 1.1. CHANGES FROM THE STUDY PROTOCOL

Reduction of the number of cries from baseline to the end of study (after 28 days), presence of infantile colic at the end of study (after 28 days), reduction of the number of regurgitations and vomiting episodes will not be evaluated since information about these secondary objectives is not collected in the eCRF.

The analysis of Bifidobacterium BB-12® effect on gut microbiota, on the fecal production of peptides from innate immune system (Calprotectina,  $\beta$ -defensin 2, LL37) and on fecal short chain-fatty acids production (butyrate and propionate) will be provided by the center to Sponsor and reported in a separate document.

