### 3.6. SAMPLE SIZE

According to the results of a previous trial that looked at a probiotic's effect on infants with CI, it is estimated that when the sample size in each group is 33, the study will have 80% power to detect an absolute difference of 35% in the treatment success rate (15% in the Placebo group and 50% in the treatment group) with a 0,05 alpha level.

The number of infants that will be included in the study is 80, with a dropout rate expected for a maximum of 20%.

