### 6.5.3. Secondary efficacy analysis

- Number of cries

Number of cries are collected daily in the diary during the entire study period.

Weekly mean of cries will be defined as the mean number of cries reported in the “Evaluation of behavior” section during the week (i.e. number of episodes/number of days with episodes) and will be described by means of descriptive statistics for continuous data.

Mean changes from baseline (i.e. mean of the first Week) to the mean of the selected week will be analyzed too.

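### SAP 6.5.3 leaves the test of number of cries to an undefined normality check and uses Week 1 only by subtraction; SAP 1.1 says the endpoint is not evaluated at all

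*SAP*

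**What the plan says.** For number of cries, SAP 6.5.3 defines a weekly mean and a change from the Week 1 mean ("Mean changes from baseline (i.e. mean of the first Week) to the mean of the selected week will be analyzed too"). For the group comparison it states that "a t-test on the change of weekly mean of cries at last Week will be performed", followed by the fallback: "In case of data not normally distributed, a Wilcoxon/Mann-Whitney test will be used".

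The SAP names no normality test, threshold or unit of assessment (pooled data, each arm, residuals), and does not say whether the check is blinded. The general methodology in 6.1 does not supply these either. No adjusted model, effect estimate or confidence interval is named for the comparison.

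No other variable in 6.5.3 has a named between-group test. Stool frequency is typical: "Summary statistics of mean stool frequency per week will be provided by means of descriptive statistics for continuous data".

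SAP 1.1, on changes from the protocol, lists reduction in the number of cries among the items that "will not be evaluated since information about these secondary objectives is not collected in the eCRF". SAP 2.2 and 5.1 still list number of cries as secondary, and 6.5.3 says it is collected daily in the diary.

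**The concern.** There are two separate weaknesses.

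1. **The data choose the test under a rule that is not written down.** One analyst may look at a histogram, another may run Shapiro-Wilk on residuals, a third may test each arm. They can report different p-values from the same data. The two tests also answer different questions, so the estimand moves with the choice.
2. **Week 1 enters only by subtraction.** A change score fixes the baseline coefficient at 1, whereas covariate adjustment estimates it. The Week 1 mean is already computed, so adjustment needs no new data.

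At stake are the reproducibility and precision of the only between-group test named in 6.5.3. The primary Chi-Square analysis is not touched.

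**Working it through.** **Inputs from the documents.** Week 1 mean as baseline, last week as endpoint, t-test or Wilcoxon (SAP 6.5.3); 33 per group, 15% versus 50%, 80% power, alpha 0.05, 80 enrolled, at most 20% dropout (SAP 3.6); 1:1 allocation (protocol synopsis). **Not given:** SD, effect and rho for number of cries. These are assumptions below.

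**The plan's own figure.** It concerns the primary endpoint and serves here only to set the sample size. Two-sided, mean proportion 0.325:
- Uncorrected n = [1.960·√(2·0.325·0.675) + 0.842·√(0.15·0.85 + 0.50·0.50)]² / 0.35² = 26.9.
- Continuity-corrected n = (26.9/4)·[1 + √(1 + 4/(26.9·0.35))]² = 32.4, so 33. The stated figure reproduces.
- After 20% dropout, 80·0.8 = 64, or 32 per arm, so 33 is a fair working size.

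**Precision, equal SDs.** In units of the common variance, the change score has 2(1−rho) and ANCOVA has 1−rho². The ratio is 2/(1+rho): 1.54 at rho 0.3, 1.33 at 0.5, 1.18 at 0.7.

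With unequal SDs, the change-score variance minus the ANCOVA variance is (SD0 − rho·SD1)², where SD0 is the baseline SD and SD1 the last-week SD. This is never negative. At rho 0.5 the ratio is 2.15 if SD1 is 0.7 of SD0 and 1.10 if it is 1.3 times SD0.

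**Power, normal data.** Suppose the change-score test has 80% power, so its standardised effect is 1.960 + 0.842 = 2.802. ANCOVA power is Φ(2.802·√(2/(1+rho)) − 1.960):

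| rho | Φ argument | ANCOVA power | gain over 80% |
|---|---|---|---|
| 0.2 | 3.617 − 1.960 | 95% | 15 |
| 0.3 | 3.475 − 1.960 | 93.5% | 13.5 |
| 0.5 | 3.235 − 1.960 | 90% | 10 |
| 0.7 | 3.039 − 1.960 | 86% | 6 |
| 0.8 | 2.954 − 1.960 | 84% | 4 |

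**Power of the whole planned rule, by simulation.** Assumptions: 33 per arm, additive effect of 0.6 SD, 2,000 runs, Shapiro-Wilk at 0.05 on residuals as the switch.

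| Assumed data | rho | Planned | Ordinary ANCOVA |
|---|---|---|---|
| Normal | 0.3 | 52% | 70% |
| Normal | 0.5 | 67% | 78% |
| Gamma, shape 2 | 0.5 | 71% | 78% |
| Gamma, shape 2 | 0.7 | 89% | 90% |
| Lognormal, sigma 0.8 | 0.3 | 79% | 72% |
| Lognormal, sigma 0.8 | 0.5 | 91% | 79% |
| Lognormal, sigma 0.8 | 0.7 | 98% | 89% |

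For lognormal data rho is on the log scale. Each power has a simulation standard error of up to √(0.25/2000) = 1.1 points. A repeat of the lognormal case with 4,000 runs put the gaps at 7, 11 and 10 points, so about 7 to 11 is a fair summary. Rank ANCOVA beat the planned rule in all nine settings (three shapes, three values of rho). Against ordinary ANCOVA it lost about 2 to 3 points with normal data.

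**Type I error.** With that switch rule fixed (20,000 runs, 33 or 40 per arm, four shapes), the planned procedure rejects in 4.9% to 5.4% of null trials. If the choice stays open and the smaller p-value is taken, the rate is about 5.8% to 7.2%.

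**How often the choice matters.** At a 0.6 SD effect and rho 0.5 or 0.7, the two tests disagree on significance in 4% to 7% of trials with normal data and 8% to 12% with gamma-skewed data.

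**The case against.** The strongest reply is that a t-test on change is valid in a randomised trial, that the protocol words this endpoint as a decrease from baseline, and that the rank fallback protects against skew. The outcome is an episode count averaged over days and bounded below, so skew is plausible, and under strong skew the planned rule beats ordinary ANCOVA. This stands. It rules out a flat statement that the plan loses power, and it is why plain ANCOVA alone is not the best replacement test.

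Three stronger readings are tempting and not supported:
- **That the switch seriously inflates type I error.** Under a fixed rule it stays near 5%. Only choosing the smaller p-value raises it, and then to about 7% at most in the shapes tried.
- **That subtracting baseline adds noise unless rho is very high.** Compared with the final value alone, the change score has 2(1−rho) times the variance, so with equal SDs it is already better above rho 0.5. The inefficiency is relative to ANCOVA.
- **That the trial's main conclusion is at risk.** The primary endpoint has its own test, and SAP 6.1 plans no multiplicity procedure through which this result could affect it.

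Two further objections hold. If SAP 1.1 governs, there is no test to repair. And 6.5.3 divides episodes by days with episodes, so cry-free days drop out and an infant with none in the last week has no defined mean. Changing the test does not cure that.

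**Conclusion.** The point holds in limited form. The undefined switch is a plain gap in prespecification: the text fixes neither the test nor the estimand. The inefficient use of Week 1 is real for roughly normal data, at about 4 to 15 power points for rho from 0.8 to 0.2, given equal SDs and a change-score test at 80% power. It shrinks towards nothing as rho approaches 1, and the comparison with ordinary ANCOVA reverses under strong assumed skew. No single figure can be given, because the documents supply no SD, effect or rho. The finding also depends on 6.5.3, not SAP 1.1, being the operative text. It is worth correcting because correction is cheap, but it concerns one secondary endpoint and its effect on the main conclusion is small.

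**What to change.** 1. Reconcile SAP 1.1 with 6.5.3: state whether number of cries is available and will be compared. If not, delete the test.
2. If the comparison is kept, replace the t-test and its fallback with one rule, for example: *The groups will be compared by rank-based ANCOVA of the last-week mean number of cries on treatment and Week 1 mean, which gives the p-value. The ANCOVA-adjusted mean difference with 95% CI will be reported in all cases as the estimate. No normality test will determine the method.*
3. In the same edit, state how cry-free days and a last week without episodes enter the mean.

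The cost is SAP wording, with no new data. There are two downsides: rank ANCOVA gives up about 2 to 3 power points against ordinary ANCOVA if the data are normal, and its p-value is not on the scale of the reported mean difference, so the two can occasionally point different ways. If the planned comparison has already been run, report it with the criterion actually used, and label the adjusted analysis as added afterwards.

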Criteria for evaluation	
Primary efficacy variable
 
The primary efficacy variable was the proportion of successful treatments, defined as a 50% or greater reduction in the average daily duration of crying episodes after 28 days of treatment.
 
Secondary efficacy variables
 
 • Decrease from baseline in the number of crying episodes and in the persistence of colics at the end of the study (day 28) • Decrease in the number of regurgitation and vomiting episodes • Number of respiratory, gastrointestinal, cutaneous and urinary infections during the study • Number of bowel movements • Consistency of fecal mass using the Bristol scale • Effects of BB-12 on intestinal microbiota • Variations of the intestinal production of innate immunity peptides (calprotectin, β defensin type 2, LL37) and short-chain fatty acids (butyrate e propionate) 
Safety variables
 
Safety was assessed based on the results of physical exams and on the incidence of adverse events (AE).

Statistical methods	
The following analysis sets were defined:
 
 • Per Protocol Set (PP): all randomized patients who completed the study without any significant protocol violation. • Intention to Treat Set (ITT): all randomized patients who received at least one dose of study treatment. • Safety Set: all randomized patients who received at least one dose of study treatment. 
Patients were analyzed according to the treatment received.

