## Statistical Analysis Plan

Sponsor:

Protocol number:

The primary efficacy analysis will be performed on the ITT population and on the PP population as supportive. The secondary efficacy analysis will be performed only on the ITT population. The safety analysis will be performed on the Safety population.

Patients violating the criteria defined above will be excluded from any analyses.

The assignment of patients to analysis populations will be summarized before the database lock in the Patient Validation Document. Final assignment of patients to analysis populations will be approved by the Sponsor study team.

The list of protocol deviations leading to the exclusion from the analysis populations is reported in the Protocol Deviation Handling Document (PDHD).

Non-protocol deviations (NOPDs) detected through SAS® programming are not protocol violations but they lead to exclusion from analysis populations; they are listed in the following Table 3-2:

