#### SECONDARY EFFICACY PARAMETERS

- Number of cries from baseline to the end of study (after 28 days) and presence of infantile colic at the end of study (after 28 days).
- Number of regurgitation and vomit.
- Number of infections of the respiratory system, gastrointestinal system, urinary system or skin during the study period.
- Daily evacuative frequency.
- Daily consistency of the fecal mass, evaluated through Bristol stool scale.

	Statistical Analysis Plan
	Sponsor:
	Protocol number:

- Bifidobacterium BB-12® effect on gut microbiota, on the fecal production of peptides from innate immune system (Calprotectina,  $\beta$ -defensin 2, LL37) and on fecal short chain-fatty acids production (butyrate and propionate).

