## 6. DEFINITION AND GENERAL METHODOLOGY

### 6.1. GENERAL METHODOLOGY

All statistical tables, listings and figures will be produced using SAS® for Windows release 9.4 (64-bit) or later (SAS Institute Inc., Cary, NC, USA). Continuous data will be summarized by mean,

	Statistical Analysis Plan
	Sponsor:
	Protocol number:

standard deviation (SD), median, 1st and 3rd quartile, minimum and maximum. Categorical data will be presented by absolute and relative frequencies (n and %) or contingency tables.

Percentages will be computed considering patients with non-missing information, if not differently specified.

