## 6.5. EFFICACY EVALUATION

Efficacy data will be summarized by treatment. Primary variables will be analyzed on the ITT and PP populations while secondary variables will be analyzed on the ITT population only.

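### Stool frequency is a named secondary efficacy endpoint, but the SAP pre-specifies no BB-12 versus placebo difference or confidence interval for it and does not say it is descriptive only

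*SAP*

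**What the plan says.** The protocol synopsis, under Criteria for evaluation, lists "Number of bowel movements" among the secondary efficacy variables. SAP 5.1 lists "Daily evacuative frequency" among the secondary efficacy parameters.

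SAP 6.5.3 then plans two things for this endpoint. The first is change from Week 1: "Mean changes from baseline (i.e. mean of the first Week) to the mean of the selected week will be analyzed". The second is weekly description: "Summary statistics of mean stool frequency per week will be provided by means of descriptive statistics for continuous data". SAP 6.5 adds a general rule, "Efficacy data will be summarized by treatment", and SAP 4 fixes the analysis set: "The secondary efficacy analysis will be performed only on the ITT population". SAP 6.1 defines continuous summaries as the mean plus "standard deviation (SD), median, 1st and 3rd quartile, minimum and maximum". That list contains no between-arm difference and no confidence interval.

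For number of cries, SAP 6.5.3 goes one step further: "in order to compare the two groups of patients, a t-test on the change of weekly mean of cries at last Week will be performed", with a Wilcoxon/Mann-Whitney test as fallback.

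**The concern.** In a placebo-controlled trial, an efficacy endpoint is informative through its contrast with placebo. Here the only change measure planned is from Week 1 to later weeks within each arm. Infants enter at 7 weeks of age or younger and are followed for 5 weeks, so bowel habit may shift with age whatever the product does. The documents give no figure for such a shift, so this is a possibility and not an established size. Any shift of this kind, or any regression towards the mean after entry, would be part of the BB-12 arm's own change.

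What is at stake is modest but concrete. A named secondary endpoint would be reported with no estimate of the BB-12 effect and no measure of its precision. Because no method is fixed, a comparison could also be chosen after the data have been seen.

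**Working it through.** **Does the text already contain a comparison?** The one candidate is the statement in SAP 6.5.3 that mean changes in stool frequency will be analysed. The entry for number of cries uses the same verb for its own mean changes, then introduces the test of the two groups as a further step. In the SAP's own usage, analysing the changes does not include comparing the arms. No other section supplies the comparison: SAP 6.5.4 (exploratory) and 6.7 (subgroups) are marked not applicable, and the protocol synopsis names a test only for the primary variable. SAP 1.1 says reduction in the number of cries will not be evaluated, which sits awkwardly with the planned test. That affects whether the test is run, not how the wording reads.

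**Are the data for a comparison available?** Yes. Stool frequency is recorded daily in the diary. Week 1 runs from T0 to T1 and randomization is at T1, so the Week 1 mean is a pre-treatment covariate. The last week runs from T4 to T5.

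**How precise would a comparison be?** The plan states no figure for stool frequency, so there is none to reproduce.

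Inputs:
- Infants per arm, n: 80/2 = 40 with no dropout. With the 20% maximum dropout in SAP 3.6, 80 × 0.80 = 64, so 32 per arm. Allocation is 1:1 (protocol synopsis, Methodology).
- Correlation r between Week 1 and last-Week means: not in the documents; assumed 0.3, 0.5 and 0.7.
- SD of the weekly mean: not in the documents; results are in SD units, with equal SD assumed in both weeks and both arms.

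Formulas for the 95% CI half-width:
- ANCOVA on the Week 1 mean: t(0.975, 2n − 3) × √(2(1 − r²)/n)
- Raw difference in change: t(0.975, 2n − 2) × √(4(1 − r)/n)

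Worked case, n = 40 and r = 0.7. ANCOVA: 1.991 × √(2 × 0.51/40) = 1.991 × 0.160 = 0.32 SD. Raw change: 1.991 × √(4 × 0.3/40) = 1.991 × 0.173 = 0.34 SD.

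Worked case, n = 32 and r = 0.3. ANCOVA: 2.000 × √(2 × 0.91/32) = 2.000 × 0.238 = 0.48 SD. Raw change: 1.999 × √(4 × 0.7/32) = 1.999 × 0.296 = 0.59 SD.

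| n per arm | r | ANCOVA half-width (SD) | Raw-change half-width (SD) |
|---|---|---|---|
| 40 | 0.3 | 0.42 | 0.53 |
| 40 | 0.5 | 0.39 | 0.45 |
| 40 | 0.7 | 0.32 | 0.34 |
| 32 | 0.3 | 0.48 | 0.59 |
| 32 | 0.5 | 0.43 | 0.50 |
| 32 | 0.7 | 0.36 | 0.39 |

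ANCOVA is the more precise in every row. The half-widths describe what the added estimate would deliver; they do not measure harm from leaving it out.

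**The case against.** The strongest reply is that little is lost. Efficacy data are summarized by treatment, so BB-12 and placebo stand in adjacent columns and a drift common to both would show in both. From each arm's mean, SD and n for the last week, a reader could work out a difference and an approximate interval. Neither document gives stool frequency a direction or a hypothesis, whereas crying is framed as a reduction. Infections, stool consistency, mood, sleep, temper and feeding also have no named test, so this looks more like a choice to describe than a slip. The trial is sized for the primary endpoint only, and SAP 6.1 marks multiplicity as not applicable. Descriptive-only secondary endpoints are legitimate.

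Much of that stands. A reader might infer that the planned output cannot answer the question at all, or that the plan as a whole confuses age with product effect. The documents support neither: the placebo column is there, and the confusion arises only if the BB-12 column is read alone. A reader might also want to attach a false-positive rate to the within-arm change. SAP 6.5.3 plans no within-arm test or interval for stool frequency, and the SD, correlation and drift needed are not given, so any such rate would describe a hypothetical misuse.

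The reply does not remove the gap. The SAP nowhere says stool frequency is descriptive only; it lists it under efficacy and gives another secondary endpoint a group test. A difference that each reader must reconstruct is not pre-specified, and one reconstructed from the last-week summaries takes no account of Week 1. The protocol available is an English synopsis of a fuller Italian document, so further text on secondary endpoints may exist there; the SAP, which should carry the method, does not.

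**Conclusion.** The point holds as a reporting and pre-specification gap on one secondary endpoint. The plan delivers by-arm summaries, but no planned estimate of the BB-12 minus placebo difference in stool frequency and no measure of its uncertainty. The reading of the text rests on no assumed figure.

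A single model would give that difference to within about ±0.32 to ±0.48 SD, against ±0.34 to ±0.59 SD for a raw difference in change. These ranges assume 32 to 40 infants per arm, a correlation of 0.3 to 0.7 and equal SDs. They say nothing about whether a product effect or an age effect exists. This is a cheap improvement, not a flaw in the trial's main conclusion: the primary analysis, sample size and safety evaluation are untouched.

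**What to change.** In SAP 6.5.3, under stool frequency, add:

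*Mean daily stool frequency in the last Week will be compared between arms on the ITT set by ANCOVA with the Week 1 mean as covariate. The adjusted difference (BB-12 minus placebo) and its 95% CI will be reported as a supportive estimate, with no confirmatory claim.*

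Keep the weekly summaries as description. Since the SAP sets no rule for missing data, report how many infants per arm have both diary weeks and so enter the model.

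The cost is a short SAP addition and one model on diary data already collected, with no extra infants or visits. ANCOVA differs from the t-test on change used for number of cries; the gain is the narrower interval shown above. The downside is one more secondary estimate without multiplicity adjustment, which is why it is labelled supportive. If the sponsor prefers no comparison, the minimum is to state that stool frequency is descriptive and supports no efficacy claim. That closes the ambiguity but leaves the difference unestimated.

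### Scoring stool consistency as any occurrence of each Bristol type in a week ties it to stool count and diary completeness, so a frequency difference can be misread as a consistency difference

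*SAP*

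**What the plan says.** Stool consistency is a secondary efficacy variable in both documents. The protocol synopsis lists "Consistency of fecal mass using the Bristol scale" and names no summary measure. SAP 5.1 lists "Daily consistency of the fecal mass, evaluated through Bristol stool scale".

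The summary is defined only in SAP 6.5.3, as the count and percentage of infants who "reported at least one stool sample of each type per week". The same item notes that an infant may have more than one consistency recorded on a day, depending on how many stools there were, and that "all the information collected will be analyzed". It names no share of stools, typical type, change from baseline or between-arm test, and no adjustment for the number of stools or diary days.

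Stool frequency is a separate secondary variable in the same section: "Stool frequency will be evaluated as the mean of total daily stools reported per week", with change from the first week. Mood, listed there among other diary data, is summarised as the number and "the proportion of infants who reported at least one mood of each type per week". SAP 6.1 marks the handling of missing data and of drop-outs as not applicable.

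**The concern.** Each recorded stool is a further chance to score a given type. An infant with more stools, or with more completed diary days, is therefore more likely to count as positive for any type, even if the mix of types is unchanged. Two readings of the table could go wrong:

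- If the product changes stool frequency, the consistency table can move when consistency has not.
- If a type is common, nearly every infant may have it at least once in a week in both arms, and a real fall in its share may not show.

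Consistency is a stated objective, recorded daily by parents for five weeks. The other daily diary measures in SAP 6.5.3 (cries, stool frequency, sleep, temper, feeding) each get a weekly mean with change from Week 1. Consistency and mood are reduced to any occurrence, with no change from baseline.

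**Working it through.** **Inputs.** The definition comes from SAP 6.5.3. The plan states no figure for this variable, so there is none to reproduce. Neither document gives stool frequency, the distribution over Bristol types, or the within-infant correlation of type. All three are assumed below and varied.

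**Formulas.** Let p be the true share of stools of a given type and n the stools recorded in the week (7 × stools per day with a complete diary).

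- Independent stools: P(at least one) = 1 − (1 − p)^n.
- Clustered stools, within-infant correlation ρ (beta-binomial): P(at least one) = 1 − B(a, b + n)/B(a, b), where B is the beta function, s = 1/ρ − 1, a = p·s and b = (1 − p)·s.

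Both rise with n for any p strictly between 0 and 1, so the direction of the problem needs no outside figure.

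**1. Frequency differs, consistency does not.** At p = 10% in both arms and independent stools, 2 a day gives 1 − 0.9^14 = 77.1% and 4 a day gives 1 − 0.9^28 = 94.8%. Repeating this for other shares and correlations:

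| Share in both arms | ρ = 0 | ρ = 0.1 | ρ = 0.3 | ρ = 0.5 |
|---|---|---|---|---|
| 5% | 51.2 vs 76.2 | 35.9 vs 48.6 | 22.4 vs 27.9 | 15.2 vs 18.0 |
| 10% | 77.1 vs 94.8 | 59.6 vs 74.1 | 40.2 vs 48.4 | 28.4 vs 33.0 |
| 20% | 95.6 vs 99.8 | 84.8 vs 93.8 | 65.3 vs 74.2 | 49.6 vs 56.0 |

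Entries are the percentage of infants scored positive at 2 versus 4 stools a day. At a 10% share the spurious gap runs from about 18 points (ρ = 0) to about 5 points (ρ = 0.5). A smaller contrast gives less: at 10%, independent, 2 versus 3 a day gives 77.1% versus 89.1%, or 12 points.

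**2. Diary days act the same way.** At p = 10% and 2 stools a day, independent, 7 recorded days give 77.1%. If only 4 days are recorded (an assumed number), n = 8 and the result is 1 − 0.9^8 = 57.0%.

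**3. Consistency differs, frequency does not.** Halve a type from 60% to 30% of stools at 3 a day (n = 21):

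| ρ | 60% share | 30% share |
|---|---|---|
| 0 | 100.0% | 99.9% |
| 0.1 | 100.0% | 97.6% |
| 0.3 | 98.5% | 85.0% |
| 0.5 | 92.8% | 69.2% |

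The halving disappears if stools are independent but shows clearly at ρ = 0.3 or more. At 1 stool a day, halving from 20% to 10% shows 79.0% versus 52.2% even with independence. The ceiling is thus confined to common types, at least moderate frequency and little clustering.

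**4. The alternative measure.** The expected percentage of an infant's stools that are of the type is n·p/n = p, whatever n is and whether or not stools cluster. It reads 10% versus 10% in step 1 and 60% versus 30% in step 3. A simulation of step 1 with independent stools gave 10.0% versus 10.0%.

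**The case against.** The strongest defence is that little depends on this table. The variable is secondary and descriptive, SAP 6.5.3 plans no test of it, and the primary endpoint is untouched. Mean stool frequency is also reported by arm with change from Week 1, so a reader can see whether frequency differs. If it does not, the frequency artefact has no systematic source. All of this stands. A reader might infer that consistency cannot be separated from frequency at all, or that a false-positive result is at risk, and the documents support neither. What remains is that seeing a frequency difference does not tell the reader how much of the consistency difference it explains.

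The size can also be challenged. The 18-point gap needs independent stools and a doubling of frequency between arms. Repeated stools from one infant plausibly resemble each other, and nothing in the documents says that such a contrast is expected. This stands too, and is why a range is given.

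A reader might also infer that common types will be near 100% in both arms. Step 3 shows that this is conditional. Because every type is tabulated, a fall in a common type may also appear as a rise in rarer ones.

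Mood might seem to share the defect. It has no link to stool count, and it is not among the secondary efficacy parameters in SAP 5.1. Only loss of information and dependence on the number of entries could apply.

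Finally, the diary form is not in the documents, so it cannot be confirmed that a type is stored for every stool. The fix must allow for that.

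**Conclusion.** The concern holds as a low-severity point. The only planned summary of stool consistency depends on stool count and diary completeness, and nothing else in either document supplies a per-stool summary or an adjustment. That follows from the definition alone.

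The size does not. In the illustration with a 10% share and 2 versus 4 stools a day, identical consistency produces a gap of about 5 to 18 points for within-infant correlations from 0.5 down to 0. Masking at the ceiling is real only for common types with little clustering. The consequence is a table that may be misread or say little. No test, and no conclusion on the primary endpoint, is affected.

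**What to change.** For each infant and week, compute the percentage of recorded stools that are of each Bristol type. If the diary does not store a type for every stool, use the percentage of recorded types and say so. Summarise these percentages by arm with change from Week 1, and state how many infants have no recorded stool in a given week, since they have no percentage. Keep the planned table as supplementary.

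A mean Bristol score is optional at most: the scale is ordinal, and equal numbers of types 1 and 7 would average 4.

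As a minor addition, summarise mood as the proportion of recorded diary days with each mood, which loses less information than any occurrence in the week.

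The cost is a small amount of derivation from diary data the SAP says are collected, plus one extra table. Data collection, sample size and the primary analysis do not change.
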